## 4 STUDY DESIGN

# 4.1 Description of study design

This is a multi-center, open label, phase II study evaluating BGJ398 anti-tumor activity in advanced or metastatic cholangiocarcinoma patients with FGFR genetic alterations. All patients will receive BGJ398 once daily on a three week on (21 days), one week off (7 days) schedule in 28-day cycles. Up to approximately 160 patients in total will be enrolled on the study.

The study has 3 cohorts. Cohort 1 will have approximately 120 patients with advanced or metastatic cholangiocarcinoma: 106 with FGFR2 gene fusions or translocations and 14 with other FGFR genetic alterations enrolled under the original protocol and amendment 1.

Cohort 2 will have approximately 20 patients with advanced or metastatic cholangiocarcinoma with specific FGFR genetic alterations (refer to Section 5.2).

Cohort 3 will have up to approximately 20 patients with advanced or metastatic cholangiocarcinoma with FGFR2 gene fusions or translocations who have received a prior FGFR inhibitor excluding BGJ398 (infigratinib). Unlike Cohorts 1 and 2, patients are allowed to have previous treatment with an FGFR inhibitor (either selective [excluding BGJ398] or nonspecific), as long as the required washout of at least 5 half-lives is met.

In order to assess the antitumor activity of BGJ398, patients in all cohorts will be evaluated for tumor response radiographically every 8 weeks until disease progression or discontinuation from study using RECIST 1.1 criteria.

# Molecular pre-screening

Documented evidence of FGFR2 gene fusions or translocations or other FGFR genetic alterations is required in order to begin study related screening procedures. In addition, the patient may have additional molecular testing performed on the provided tissue sample.

- Evidence can be demonstrated by either locally available data (local laboratory or institution-designated sequencing facility) or through the submission of an archival or newly obtained tumor sample to a QED Therapeutics designated central laboratory for analysis. Tissue requirements are described in Section 7.1.1.
- If local data is not available, the patient must sign the molecular prescreening consent to allow for the collection and/or submission of samples for local testing at an institution designated laboratory or sequencing facility or to the QED Therapeutics designated central laboratory for analysis.

If local data or the results of the central analysis meet inclusion criteria, the patient can proceed with the screening procedures.

## Screening

Screening assessments must be completed within 21 days prior to the first dose of study treatment except for the radiological tumor assessment which should be performed within 28 days prior to the first dose (Section 7.1.2).

## Treatment period

Treatment period will begin on Cycle 1 Day 1 and will continue until disease progression, unacceptable toxicity, withdrawal of informed consent, or death (Section 7.1.3).

# End of treatment (EOT)

The EOT visit occurs within 14 days after of the decision to discontinue study treatment (Section 7.1.4). All participating patients must complete this visit even if they had to discontinue prematurely.

## Follow-up

All patients will be followed up as described in Section 7.1.6.

## 30-day safety follow-up period

At a minimum, all patients must complete the safety follow-up assessments 30 days after their last dose of BGJ398 (Section 7.1.6).

# Disease progression follow-up period

All patients enrolled in the study who discontinue study treatment for any reason other than disease progression will have a tumor assessment every 8 weeks, until disease progression or the initiation of subsequent anticancer therapies, or death, whichever occurs first

# Survival follow-up period

All patients enrolled in the study will be followed for survival at least every 4 months for up to 5 years after discontinuation of treatment (Section 7.1.6).

# 4.2 Timing of interim analyses and design adaptations

Safety and efficacy data will be continuously monitored by QED Therapeutics in conjunction with the investigators for decision-making purposes.

For Cohort 1, one analysis was performed before amendment 2 based on the 61 patients enrolled in the study (30 Jun 2016). Protocol amendment 2 restricted enrollment to patients with FGFR2 fusions or translocations, and the formulation was changed from FMI I to FMI III.

After 20 patients had been treated with FMI III (for at least one cycle) based on amendment 2, a comprehensive review of all relevant data such as PK, safety, dose interruptions/reductions, and available efficacy was performed. Upon review of the data, it was decided to continue dosing all subsequent patients treated with FMI III at 125mg on a 3 weeks on. 1 week off schedule.

In addition, two formal interim analyses for Cohort 1 are planned after amendment 3:

- The first was conducted when the patients enrolled prior to amendment 2 and the patients in Cohort 1 with planned extensive PK sample collection (regardless of whether extensive PK samples were actually collected) had been followed up for at least 10 months after their initial exposure to BGJ398.
- The second will be conducted when all the patients who received BGJ398 at the time of the first formal interim analysis have at least 10 months follow-up after their initial exposure to BGJ398.

Additionally, for Cohorts 2 and 3, review of data will be performed after a total of 15 patients in either Cohort 2 or 3 have been treated with FMI IV for at least one cycle. A formal interim analysis will be conducted for Cohort 3 when the first 10 patients who receive study treatment have the potential to complete their second scheduled scan; this analysis is to determine if an additional 10 patients will be added to the cohort (see Section 10.8.2).

# 4.3 Assessment of potential mechanisms of resistance

Patients may have tumor tissue and blood samples collected at baseline and at disease progression to study the mechanisms of drug treatment resistance.

# 4.4 Definition of end of the study

End of study is defined as the time when the last patient completes the survival follow-up as described in Section 7.1.6 and/or when the study is terminated early.

# 4.5 Early study termination

The study can be terminated at any time for any reason by QED Therapeutics. Should this be necessary, the patient should make every effort to complete their final visit. The same assessments should be performed as described in Section 7.1.4 and Section 7.1.5 for a prematurely withdrawn patient. The investigator may be informed of additional procedures to be followed in order to ensure that adequate consideration is given to the protection of the patient's interests. The investigator will be responsible for informing IRBs and/or ECs of the early termination of the trial.

## 5 POPULATION

# 5.1 Patient population

Adult patients with histologically or cytologically confirmed advanced or metastatic cholangiocarcinoma with FGFR2 gene fusions or translocations or other FGFR genetic alterations will be enrolled. Patients must have received at least one prior regimen containing gemcitabine with or without cisplatin for advanced/metastatic disease. Patients should have had evidence of progressive disease following their prior regimen or if prior treatment was discontinued due to toxicity must have continued evidence of measurable disease.

Evidence of FGFR2 gene fusion or other FGFR genetic alterations must be documented through either institutional data or central laboratory testing (please refer to Section 7.1.1 for further details).

Patients enrolled in this study are not permitted to participate in additional parallel investigational drug or device studies. Patients who do not initially meet all of the inclusion or exclusion criteria may be re-screened for consideration in the trial. If a patient is rescreened, the same patient ID number should be used (see Section 7.1.2.2).

Only patients who have documented evidence of FGFR2 gene fusion or other FGFR genetic alterations will be allowed to enter screening. The investigator or designee must ensure that only patients who meet all the following inclusion and none of the exclusion criteria are offered treatment in the study.

#### 5.2 Inclusion criteria

Amended Protocol Version 06 (15-Jan-2020)

Patients eligible for inclusion into all cohorts of this study have to meet all of the following criteria, unless otherwise noted:

- 1. Patients with histologically or cytologically confirmed cholangiocarcinoma at the time of diagnosis. Patients with cancers of the gallbladder or ampulla of Vater are not eligible.
- 2. Written documentation of local laboratory or central laboratory determination of the following FGFR gene alterations from a sample collected before BGJ398 treatment:
  - Cohort 1: FGFR2 gene fusions or translocations.
  - Cohort 2: one of the following:
    - a. FGFR1 fusions or translocations.
    - b. FGFR3 fusions or translocations.
    - c. FGFR1/2/3 mutation known to be an activating mutation and noted in Appendix 4 (Section 14.4; for mutations not listed in Appendix 4, enrollment may be allowed with written pre-approval of the QED Medical Monitor).
  - Cohort 3: FGFR2 gene fusions or translocations.
- 3. An archival tissue sample must be available with sufficient tumor for central FGFR gene alteration molecular testing if written documentation is provided from a local laboratory, unless agreed upon between QED Therapeutics and the Investigator. However, if an archival tissue sample is not available, a newly obtained (before start of treatment) tumor biopsy may be submitted instead. If written documentation of FGFR gene alteration in tumor tissue is available from the central laboratory, an additional tumor sample does not need to be submitted for central FGFR gene alteration molecular testing. Note: All enrolled patients should have determination of FGFR gene alteration by the central laboratory as confirmation of local laboratory testing, but this central confirmation is not required prior to enrollment in the study.
- 4. Evidence of measurable disease according to RECIST Version 1.1.
- 5. Patients must have received at least one prior regimen containing gemcitabine with or without cisplatin for advanced/metastatic disease. Patient should have had evidence of progressive disease following their prior regimen, or if prior treatment was discontinued due to toxicity must have continued evidence of measurable disease.
- 6. Patients  $\geq$  18 years of age of either gender.
- 7. ECOG performance status < 1 (Patients with ECOG performance status of 2 may be considered on a case-by-case basis after discussion with QED Therapeutics).

- 8. Able to read and/or understand the details of the study and provide written evidence of informed consent as approved by IRB/EC.
- 9. Recovery from adverse events of previous systemic anti-cancer therapies to baseline or Grade 1, except for:
  - a. Alopecia
  - b. Stable neuropathy of < Grade 2 due to prior cancer therapy
- 10. Able to swallow and retain oral medication.
- 11. Willing and able to comply with scheduled visits, treatment plan and laboratory tests.

#### 5.2.1 Additional inclusion criteria for Cohort 3

12. Documented prior treatment with FGFR inhibitor other than BGJ398/infigratinib.

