Cohort 2 will enroll approximately 20 patients with advanced or metastatic cholangiocarcinoma with FGFR genetic alterations other than FGFR2 gene fusions or translocations (specifically FGFR1, 2, or 3 activating mutation or FGR1 or 3 fusions or translocations) who have evidence of radiologic progression following a cisplatin-and gemcitabine-containing regimen for advanced disease or a gemcitabine-containing regimen for those who are considered intolerant to cisplatin. While FGFR2 fusions are the predominant FGFR genomic alteration seen in cholangiocarcinoma, other FGFR alterations do occur. In Cohort 1, 14 patients were enrolled with non-FGFR2 fusions, including 7 with FGFR1, 2, or 3 amplifications and 7 with FGFR2 mutations. In the 7 patients with FGFR2 mutations and response data, 6 (86%) had stable disease (based on central review). Patients such as these with other FGFR alterations have no targeted treatment options, and these preliminary results compare favorably with outcomes for current standard of care. Therefore, Cohort 2 will enroll patients with known FGFR1, 2, or 3 activating mutation (See Appendix 4 [Section 14.4] for details of allowed mutations) or FGFR1 or 3 fusions or translocations.

Cohort 3 will enroll up to approximately 20 patients with advanced or metastatic cholangiocarcinoma with FGFR2 gene fusions or translocations after previous treatment with gemcitabine-containing regimen followed by progression on an FGFR inhibitor (excluding BGJ398). As multiple FGFR inhibitors (both selective and non-selective) have entered into clinical development, it is important to understand the clinical efficacy when compounds are used in sequence. Consideration of the diverse mechanisms of action and binding pocket interactions for FGFR inhibitors suggests that BGJ398 may have activity when used after other FGFR inhibitors (both selective and non-selective). The potential for activity of BGJ398 in this population with limited therapeutic options supports study of BGJ398 in patients after treatment with and progression on other FGFR inhibitors. Approximately 10 patients will initially be enrolled and an additional

10 patients will be added if  $\geq$ 4 patients of the 10 are assessed to be benefiting from study treatment as defined in Section 10.8.2.

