In Cohort 3, the same definition of benefit rate as for Cohort 2 (the percentage of patients who are progression-free at the second scheduled scan [approximately 16 weeks] or later) will be applied. The benefit rate will be estimated with 95% exact confidence interval. The planned enrollment for Cohort 3 is a maximum of 20 patients. With 20 patients, the exact 95% confidence interval half width is <23%. One interim analysis is planned when 10 patients have been dosed and have the potential to be followed up for response for at least 2 scheduled scans. If at the interim analysis,  $\geq$ 4 patients are progression-free at the second scheduled scan (after approximately 16 weeks) or later, the cohort will continue to enroll the additional 10 patients; otherwise, enrollment will stop at 10 patients. If  $\leq$ 20% patients are benefiting from the study treatment, there is <12.1% chance that the decision after the interim analysis will lead to continuing enrollment.

The percentage of patients considered to have benefited from treatment will be estimated with 95% exact binomial CI. If all 20 patients are enrolled, the exact 95% CI half width will not exceed 23%. Table 14 provides some examples of CIs corresponding to observed numbers of patients considered to have benefited from treatment. At the final analysis, if 9 of 20 patients who are progression-free at the second scheduled scan or later, the lower bound of the 95% exact CI will exclude 20%.

Table 14: 95% CI examples corresponding to observed numbers of patients considered to have benefited from treatment (Cohorts 2 and 3)

Number of patients considered to have benefited from treatment	95% Exact CI
4	(0.057, 0.437)
8	(0.191, 0.640)
9	(0.231, 0.685)
10	(0.272, 0.728)
12	(0.361, 0.809)

CI: confidence interval; PFS: progression-free survival

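### Cohort 3 is justified for patients who progressed on another FGFR inhibitor, but eligibility asks only for prior treatment, so the expansion rule's 12.1% figure does not cover the progressed population

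*Protocol*

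**What the plan says.** Protocol Section 2.2 describes Cohort 3 as patients previously treated with gemcitabine, "followed by progression on an FGFR inhibitor" other than BGJ398. It then argues that the drug's potential activity "supports study of BGJ398 in patients after treatment with and progression on other FGFR inhibitors".

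The criterion that sites enrol on is number 12, in Section 5.2.1: "Documented prior treatment with FGFR inhibitor other than BGJ398/infigratinib". It does not mention progression. The protocol summary, Table 2 (objectives), Figure 1 and SAP Section 1.1 likewise speak only of a prior FGFR inhibitor having been received. Protocol Section 4.1 says "Unlike Cohorts 1 and 2, patients are allowed to have previous treatment with an FGFR inhibitor", subject to a washout.

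Inclusion criterion 5 applies to all cohorts. It expects progressive disease after the prior regimen, with an exception: "if prior treatment was discontinued due to toxicity must have continued evidence of measurable disease".

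The decision rules are in Protocol Section 10.8.2 and SAP Section 3.2. Cohort 3 grows from 10 to 20 patients if at least 4 of the first 10 are progression-free at the second scheduled scan or later. Treatment is considered to benefit patients if the lower limit of the exact 95% interval excludes 20%, which 9 of 20 achieves. If no more than 20% benefit, "there is <12.1% chance that the decision after the interim analysis will lead to continuing enrollment".

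**The concern.** Section 2.2 asks whether this drug works after another FGFR inhibitor has failed. A patient who stopped the earlier inhibitor without progressing may still have a tumour sensitive to FGFR inhibition. Being progression-free at about 16 weeks then says little about activity after progression, yet it counts fully toward 4 of 10 and 9 of 20.

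Criterion 5 does not close the gap. If its prior regimen means the gemcitabine regimen, it says nothing about the FGFR inhibitor. If it means the most recent regimen, it still admits patients who stopped for toxicity.

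The analysis does not separate these patients either. The interim set is the first 10 dosed, and the efficacy subgroups in SAP Section 2.2.8 are prior lines, gender, age and region. The cohort could expand, or be read as showing activity after progression, because of patients who had not progressed.

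**Working it through.** **Inputs from the documents.** Interim n = 10, threshold 4; final n = 20, threshold 9; reference rate 20% (Protocol Section 10.8.2).

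**Assumed inputs.** The documents give neither the number m of non-progressed patients per 10 nor their benefit rate q. I use m = 1 to 3 and q = 30% to 60%, with progressed patients at 20%.

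**Step 1: the plan's own figure.** For X ~ Bin(10, 0.20):

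P(X ≥ 4) = 1 − (0.1074 + 0.2684 + 0.3020 + 0.2013) = 0.1209.

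The stated bound below 12.1% is reproduced. The exact interval for 9 of 20, 0.231 to 0.685, also matches Table 14.

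**Step 2: interim rule in a mixed cohort.** X = Bin(m, q) + Bin(10 − m, 0.20), so

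P(X ≥ 4) = Σ_j P(Bin(m, q) = j) × P(Bin(10 − m, 0.20) ≥ 4 − j).

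For m = 3 and q = 0.50: 0.125 × 0.0333 + 0.375 × 0.1480 + 0.375 × 0.4233 + 0.125 × 0.7903 = 0.317.

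| Assumed q | m = 1 | m = 2 | m = 3 |
|---|---|---|---|
| 20% | 12.1% | 12.1% | 12.1% |
| 30% | 13.8% | 15.8% | 17.8% |
| 40% | 15.6% | 19.7% | 24.4% |
| 50% | 17.4% | 24.0% | 31.7% |
| 60% | 19.1% | 28.5% | 39.8% |

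**Step 3: final rule, reached only through the interim.** Let A and B be the benefit counts in the first and second 10, each with m = 3 non-progressed patients. The event is A ≥ 4 and A + B ≥ 9.

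| Rate in the 3 non-progressed per 10 | P(pass interim and reach 9 of 20) |
|---|---|
| 20% (no difference) | 0.84% |
| 40% | 4.1% |
| 50% | 7.3% |
| 60% | 12.0% |

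Treating the 20 patients as a single stage would give 4.8%, 8.4% and 13.6%, against 1.0%. That overstates the risk, because enrolment stops at 10 unless the interim is passed.

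**Step 4: when there is no inflation.** Hold the cohort's average at 20%. Two patients at 50% and eight at 12.5% (2 × 0.5 + 8 × 0.125 = 2 of 10) give P(X ≥ 4) = 10.2%. Three at 40% and seven at 11.4% give 10.7%. Both are below 12.1%.

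**Step 5: a lower rate in progressed patients.** If they benefit at 10%, two of 10 at 50% give 6.7% and three of 10 at 50% give 13.1%.

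**The case against.** A reader might infer that the stated 12.1% is wrong, or that the plan breaches its own error rate. The documents do not support that. The figure is conditional on no more than 20% of patients benefiting and makes no claim about progressed patients alone. The scenarios in step 2 break that condition: with m = 3 and q of 40%, 50% or 60%, the cohort averages are 26%, 29% and 32%. Expanding more often when more enrolled patients benefit is what the rule is built to do. This part of the objection stands.

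It can also be said that Section 2.2 is the outlier. The objectives, the design text and the SAP all describe patients who received a prior inhibitor, so amending the rationale would remove the contradiction equally well. That is fair. It affects which text changes, not whether the texts disagree.

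Criterion 5 makes progression the norm and toxicity the exception. If the FGFR inhibitor was the latest regimen, most patients may have progressed on it. That narrows the gap without closing it.

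Finally, Cohort 3 objectives are exploratory and the cohort is capped at about 20 patients. A reader might speak of an inflated confirmatory type I error, but the plan makes no confirmatory claim here. What is at stake is up to 10 further patients and how the result is read.

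**Conclusion.** The rationale and the eligibility criteria describe different Cohort 3 populations, and neither another criterion nor any planned subgroup reconciles them. The 12.1% is correct for the enrolled cohort under its own condition, but it is not a safeguard for the progressed population in Section 2.2.

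With progressed patients at 20%, the chance of expanding is 14% to 40% over the assumed range, and the chance of passing both rules is 4.1% to 12.0% against 0.84% when 3 per 10 are non-progressed at 40% to 60%. The size rests entirely on an assumed share and benefit rate. It disappears if non-progressed patients also benefit at 20%, or if the cohort's average stays at 20%. The contradiction in the text does not depend on these assumptions.

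**What to change.** Reconcile Protocol Section 2.2, criterion 5 and criterion 12 so that rationale and eligibility describe the same Cohort 3 population. Either text can move, but criterion 5 should make clear which regimen it refers to.

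If eligibility stays broad:

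- Record the outcome on the prior FGFR inhibitor. Protocol Section 7.1.2.3 collects details of prior antineoplastic treatment, and SAP Section 2.3.4 summarises best response at last treatment, with time to progression only for first-line gemcitabine-based therapy. Neither shows that progression on the FGFR inhibitor, or the reason for stopping it, is captured, so the sponsor should confirm that field.
- Report the benefit rate with its exact interval separately for patients with and without documented progression on the prior inhibitor.
- Limit any statement about activity after progression to the progressed patients.

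If the decision rules are to apply to progressed patients only, keep 10 and 20 progressed patients as the denominators. Requiring 4 from a smaller group is a different rule: with 7 patients at 20%, P(X ≥ 4) is 3.3%.

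The cost is wording, one data field to confirm and a small reporting addition, with possibly slower accrual if eligibility is narrowed or if 10 and 20 progressed patients are required.

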#### 5.3 **Exclusion criteria**

Patients eligible for this study must not meet **any** of the following criteria:

- 1. Prior or current treatment with a mitogen-activated protein kinase (MEK) inhibitor (all cohorts), BGJ398/infigratinib (all cohorts), or selective FGFR inhibitor (Cohorts 1 and 2 only).
- 2. Neurological symptoms related to underlying disease requiring increasing doses of corticosteroids. Note: Steroid use for management of CNS tumors is allowed but must be at a stable dose for at least 2 weeks preceding study entry.
- 3. History of another primary malignancy except adequately treated in situ carcinoma of the cervix or non-melanoma carcinoma of the skin or any other curatively treated malignancy that is not expected to require treatment for recurrence during the course of the study.
- 4. Any other medical condition that would, in the investigator's judgment, prevent the patient's participation in the clinical study due to safety concerns or compliance with clinical study procedures.
- 5. Current evidence of corneal or retinal disorder/keratopathy including, but not limited to, bullous/band keratopathy, inflammation or ulceration, keratoconjunctivitis, confirmed by ophthalmic examination.
- 6. History and/or current evidence of extensive tissue calcification including, but not limited to, the soft tissue, kidneys, intestine, myocardium, vascular system, and lung with the exception of calcified lymph nodes, minor pulmonary parenchymal calcifications, and asymptomatic coronary calcification.

4Protocol No.

- 7. Impairment of gastrointestinal (GI) function or GI disease that may significantly alter the absorption of oral BGJ398 (eg, ulcerative diseases, uncontrolled nausea, vomiting, diarrhea, malabsorption syndrome, small bowel resection).
- 8. Current evidence of endocrine alterations of calcium/phosphate homeostasis, eg, parathyroid disorders, history of parathyroidectomy, tumor lysis, tumoral calcinosis etc.
- 9. Treatment with any of the following anti-cancer therapies prior to the first dose of BGJ398 within the stated timeframes.
  - Cyclical chemotherapy (intravenous) within a period of time that is shorter than the cycle length used for that treatment (eg, 6 weeks for nitrosourea, mitomycin-C)
  - Biological therapy (eg, antibodies including bevacizumab) within a period of time that is  $\leq 5$  t1/2 or  $\leq 4$  weeks, whichever is shorter, prior to starting study drug
  - Continuous or intermittent small molecule therapeutics within a period of time that is  $\leq 5$  t1/2 or  $\leq 4$  weeks (whichever is shorter) prior to starting study drug
  - Any other investigational agents within a period of time that is  $\leq 5$  t1/2 or less than the cycle length used for that treatment or  $\leq 4$  weeks (whichever is shortest) prior to starting study drug
  - Wide field radiotherapy (including therapeutic radioisotopes such as strontium 89) ≤ 4 weeks or limited field radiation for palliation ≤ 2 weeks prior to starting study drug
- 10. Patients who are currently receiving, or are planning to receive during participation in this study, treatment with agents that are known strong inducers or inhibitors of CYP3A4 and medications which increase serum phosphorus and/or calcium concentration are excluded. (Refer to Appendix 2 for list of prohibited medications). Patients are not permitted to receive enzyme-inducing anti-epileptic drugs
- 11. Consumption of grapefruit, grapefruit juice, grapefruit hybrids, pomegranates, star fruits, pomelos, Seville oranges, or products containing juice of these fruits, within 7 days prior to first dose
- 12. Insufficient bone marrow function
  - ANC  $< 1,000/\text{mm}^3 [1.0 \times 10^9/\text{L}]$
  - Platelets  $< 75,000/\text{mm}^3 [75 \times 10^9/\text{L}]$
  - Hemoglobin < 9.0 g/dL
- 13. Insufficient hepatic and renal function

- Total bilirubin > 1.5x ULN (for patients with documented Gilbert syndrome, direct bilirubin ≤1.5x ULN and enrollment requires approval by the medical monitor)
- AST/SGOT and ALT/SGPT > 2.5x ULN (AST and ALT > 5x ULN in the presence of liver metastases)
- Serum creatinine > 1.5x ULN and a calculated (using the Cockcroft-Gault formula [Cockcroft 1976]) or measured creatinine clearance of < 45 mL/min
- 14. Abnormal calcium or phosphorus:
  - Inorganic phosphorus outside of normal limits
  - Total serum calcium (can be corrected) outside of normal limits
  - Calcium-phosphorus product ≥55 mg²/dL²
- 15. Clinically significant cardiac disease including any of the following:
  - Congestive heart failure requiring treatment (NYHA Grade ≥ 2), LVEF < 50% as determined by MUGA scan or ECHO, or uncontrolled hypertension (refer to WHOISH guidelines)
  - History or presence of clinically significant ventricular arrhythmias, atrial fibrillation, resting bradycardia, or conduction abnormality
  - Unstable angina pectoris or acute myocardial infarction ≤ 3 months prior to starting study drug
  - QTcF > 470 msec (males and females)
  - History of congenital long QT syndrome
- 16. Pregnant or nursing (lactating) women, where pregnancy is defined as the state of a female after conception and until the termination of gestation, confirmed by a positive hCG laboratory test
- 17. Women of child-bearing potential (WOCBP), defined as all women physiologically capable of becoming pregnant, unless they are using barrier contraception and a second form of highly effective contraception during dosing and for 3 months following the discontinuation of study treatment.

WOCBP and males whose sexual partners are WOCBP must agree to use barrier contraception and a second form of highly effective contraception (Clinical Trials Facilitation Group 2014; see Appendix 5 [Section 14.5]) while receiving study drug and for 3 months following their last dose of study drug. Alternatively, total abstinence is also considered a highly effective contraception method when this is in

line with the preferred and usual lifestyle of the patient. Periodic abstinence (eg, calendar, ovulation, symptothermal, post-ovulation methods) and withdrawal are not acceptable methods of contraception.

A woman is not of child-bearing potential if she has undergone surgical sterilization (total hysterectomy, or bilateral tubal ligation or bilateral oophorectomy at least 6 weeks before taking study drug) or if she is postmenopausal and has had no menstrual bleeding of any kind including menstrual period, irregular bleeding, spotting, etc., for at least 12 months, with an appropriate clinical profile, and there is no other cause of amenorrhea (eg, hormonal therapy, prior chemotherapy).

- 18. Sexually active males unless they use a condom during intercourse while taking drug and for 3 months after the last dose of the study drug and should not father a child in this period. A condom is required to be used also by vasectomized men as well as during intercourse with a male partner in order to prevent delivery of the drug via seminal fluid.
- 19. Have amylase or lipase  $> 2.0 \times ULN$ .
- 20. Have any known hypersensitivity to calcium-lowering agents, infigratinib, or their excipients.

## 6.1.1 Additional exclusion criteria for Cohort 3

21. Known existence of a V564F mutation in the FGFR2 gene.

